## **Overview of Study**

[figure not shown]
In the proposed project we will evaluate the feasibility of IVR and assess the initial effects of IVR on symptoms, affect, and tolerance to cutaneous stimuli. In this single-arm trial, we will recruit 20 adults with CBP. Prior to their IVR experience, subjects will complete multiday baseline assessments using ecological momentary assessment (EMA) methodology to establish typical levels of symptoms and affect. They will return for two counterbalanced IVR sessions: one 10-minute and one 20-minute. Immediately after each session we will measure current symptoms and affect using valid and reliable self-report questionnaires, and we will measure changes in tolerance to cutaneous stimuli using quantitative sensory testing. We will measure symptoms and affect for 72 hours after each experimental session using EMA to determine if there is a carryover. At the completion of this study, we will continue to work with stakeholders to develop clinically relevant IVR interventions for people with CBP. Our study will have two aims:

Aim 1: Determine the feasibility and clinical usability of using IVR as an intervention for people with CBP.

Aim 2a: Examine the magnitude of the effects of IVR on symptoms, affect, and tolerance to cutaneous stimuli.

2b: Examine the effect of dosage (10 min, 20 min) on symptoms, affect, and tolerance to cutaneous stimuli.

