#### **Outcome measures**

Our study will include feasibility measures and magnitude of effect measures: Feasibility measures will examine the practicalities of investigating implementation of IVR for people with CBP and subjects' preferences and tolerance to the protocol.

Item	Measurements
Recruitment	Responses to different recruitment methods; # contacting study; # coming to study; # consented; Recruitment generating appropriate subjects; # willing to be randomized
Adherence/Fidelity	Immersion into VR (Igroup Presence Questionnaire [IPQ]); Engagement in IVR (User Engagement Scale [UES]); # of breaks; # of subjects completing study; Completeness of data collection
Burden	Length of time to complete measures, length of time for ecological momentary assessment (EMA) responses, subjects' perception of burden (open-ended questions)
Tolerance	Tolerance to IVR (Simulator Sickness Questionnaire [SSQ]); minutes in IVR experience; tolerance to Quantitative Sensory Testing (QST); open-ended question responses
Stakeholder input	Open ended questions about perceptions and preferences.

Measures for the magnitude of effect will address symptoms, affect and tolerance to cutaneous stimuli. All the proposed measures are valid and reliable measures of the proposed construct.

Item	Measurements
Symptoms	
Pain	Pain Visual Analogue Scales (VAS) (EMA and Session), PROMIS pain interference scale (Session)
Fatigue	PROMIS Daily Fatigue Scale (EMA and Session), PROMIS Fatigue Scale

Affect	(Session) Positive and Negative Affect Scale (PANAS) (EMA and Session)
Quantitative Sensory Testing (QST) (Session)	
Hyperalgesia	Mechanical Pressure Pain Thresholds (MPPTh) will be assessed using a digital pressure algometer on the right upper trapezius and right thumb MP joint. Mechanical Temporal Summation of Pain (MTSP) will be assessed using weighted pinprick stimulators. We will apply a train of 10 stimuli at the rate of 1 per second on the middle finger of the right hand, and subjects will rate the painfulness of the first, fifth, and tenth stimulus.

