#### *Protocol*

Visit 1 (remote): We will obtain informed consent. Subjects will complete surveys on demographics and symptoms (pain, fatigue) and affect. Subjects will be randomly assigned to receive the 10 min or 20 min IVR session first.

We will also upload the EMA technology onto the subject's phone or tablet. Visit 1 will take up to ~1 hour.

Multiple Baseline EMA: Visit 2 will be scheduled 1-2 weeks later. During the time between visits we will use ecological momentary assessment (EMA) technology to collect multiple measures of pain, fatigue and affect. In EMA subjects respond to prompts delivered through their cell phone or tablet ("pings") with documentation of current symptoms. It is a well-recognized method to capture immediate, synchronized experiences in subjects' natural environments. During this data collection period subjects will be "pinged" 3x daily and asked to rate their current levels of pain, fatigue, and affect. Time to complete these responses will be less than 5 minutes.

Visit 2: We will collect current pain, pain interference, fatigue and affect, and QST. Subjects will receive an IVR session lasting either 10 or 20-min depending upon randomization. They will rate their current pain, fatigue, and affect, and we will complete QST. At the end of both sessions the subjects will rate their experiences of immersion using the Igroup Presence Questionnaire, engagement using the Use Engagement Scale (UES), and simulation tolerance using the Simulator Sickness Questionnaire (SSQ). Visit 2 will take about ~1 hour.

Post Visit 2 EMA: Subjects will complete three more days of 3x a day prompts for pain, fatigue and affect.

After Visit 2 we will follow-up with subjects using EMA for at least 72 hours to determine if there is any carryover of effect of IVR. This period will also act as a washout period before returning for the third visit.

Visit 3 will be the same as Visit 2. Participants will complete 10- or 20- minutes of VR depending upon randomization. We will complete a short semi-structured interview.

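### Post-session EMA is collected to determine carryover and covers the washout, but Aim 2 states no analysis of it and does not tie symptom and affect effects to the pre-session ratings

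*Combined protocol and SAP*

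**What the plan says.** **Purpose.** The Overview of Study says: "We will measure symptoms and affect for 72 hours after each experimental session using EMA to determine if there is a carryover". The Protocol section repeats the purpose for the first session: "After Visit 2 we will follow-up with subjects using EMA for at least 72 hours to determine if there is any carryover". It sets the schedule as "Subjects will complete three more days of 3x a day prompts for pain, fatigue and affect" and adds: "This period will also act as a washout period before returning for the third visit".

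**Status of the EMA measures.** Outcome measures says: "Measures for the magnitude of effect will address symptoms, affect and tolerance to cutaneous stimuli". Under that heading, the pain VAS, the daily fatigue scale and the PANAS are each marked for use both in EMA and at sessions.

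**Possible baselines for symptoms and affect.** There are three: the Visit 1 surveys; the "multiday baseline assessments using ecological momentary assessment (EMA) methodology to establish typical levels of symptoms and affect"; and the ratings taken at Visit 2 before the headset goes on ("We will collect current pain, pain interference, fatigue and affect, and QST"), repeated at Visit 3, which is described as identical to Visit 2.

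**Analysis.** Aim 2 compares baseline with scores obtained right after the sessions. For symptoms and affect it refers to baseline symptom data and limits the comparison to the immediate effect. For QST it names pre-session levels explicitly. The dose sentence asks for an effect size between 10 and 20 minutes and names no time point. The section's only explicit mention of EMA is under Aim 1, as a completion percentage.

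**The concern.** Two gaps follow from setting the data collection against the analysis.

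First, carryover is the stated reason for the follow-up EMA, and subjects carry its burden, yet no summary, window or contrast of those data is given. Since the post-Visit 2 window is also the washout, the plan has no stated way to tell whether the first session's effect had faded before the second began.

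Second, the reference value for the immediate symptom and affect effect is left open. If it precedes Visit 2, anything left over from the first session is counted as part of the second session's effect. So is any difference between ratings made in daily surroundings and ratings made at a visit. Aim 2a is about the size of that effect.

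The feasibility aim is untouched. QST is less exposed, because its pre-session level is named.

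**Working it through.** **The text.** There is no planned figure to reproduce: the gap lies in what Aim 2 omits. The wording about scores taken after the session does not cover the EMA, because the same sentence confines itself to the immediate effect.

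**Prompts scheduled.** Baseline: 1 to 2 weeks × 3 daily = 21 to 42 per subject. After a session: 3 days × 3 = 9 per subject, a minimum, since the follow-up is for at least 72 hours.

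**Effect of the baseline choice.** Let τ be the mean immediate effect. Let λ10 and λ20 be the residuals at Visit 3 after a first session of 10 or 20 minutes, with mean λ = (λ10 + λ20)/2 and equal numbers per sequence.
- From a pre-Visit 2 baseline, Visit 2 gives τ and Visit 3 gives τ + λ. The average is τ + λ/2, so half the mean residual enters.
- The 20 minus 10 minute contrast from that baseline is (τ20 − τ10) + (λ10 − λ20)/2. It is free of residual if λ10 = λ20.
- From each visit's own pre-session rating, the residual drops out of both, provided it is equally present before and after the session.

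**Why the last day is needed.** Daily effects of 1, 0, 0 give a 72-hour mean of 1/3 and a day-3 value of 0. Daily halving (1, 0.5, 0.25) gives a mean of 0.58 and a day-3 value of 0.25. The 72-hour mean therefore measures persistence but does not check washout.

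**Precision (illustration only).** The documents give no variances. I assume 20 completers and split the variance of a single rating (total 1) into subject, subject-by-phase p, subject-by-day d and prompt e. The five sets are (.5, .1, 0, .4), (.5, .1, .1, .3), (.5, .2, 0, .3), (.4, .1, .1, .4) and (.6, .05, .05, .3), each with 21 and 42 baseline prompts.
- Baseline mean: vb = p + d/days + e/prompts. 72-hour mean: v = p + d/3 + e/9. Day 3: v = p + d + e/3. Half-width = 2.093 × √((vb + v)/20).
- Example, second set, 21 prompts: vb = 0.1 + 0.1/7 + 0.3/21 = 0.129. The 72-hour v = 0.167 gives a half-width of 0.25; the day-3 v = 0.300 gives 0.31.
- Over all sets: 0.19 to 0.31 for the 72-hour mean, per dose if EMA follows both sessions; 0.24 to 0.34 for day 3 with 20 subjects. After Visit 2 alone, the 20 subjects are a mix of both doses.
- Visit 3 minus Visit 2 pre-session rating, 2.093 × √(2(p + d + e)/20): 0.42 to 0.51.

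**Price of the pre-session baseline.** SE at one visit is √(2e/20) = 0.173 to 0.200 from the pre-session rating, against √((vb + p + d + e)/20) = 0.152 to 0.191 from the EMA baseline. The ratio runs from 0.92 to 1.15, so precision does not decide between them.

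**The case against.** **EMA after Visit 3.** The Protocol section has a follow-up entry only after Visit 2, and a reader might infer that EMA stops there. Each subject would then show persistence for one dose only, 9 prompts per subject would go uncollected, and the dose comparison of persistence would be about 10 against 10. The documents do not support this. The Overview promises EMA after each session, and Visit 3 is described as the same as Visit 2; the simplest reading is that EMA is repeated. A figure missing from the extracted text may also settle it. What stands is a wording point.

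**The multiday baseline may be deliberate.** It is designed to capture typical levels, and Aim 2 words the symptom and QST comparisons differently. This is fair, and change from typical level should be kept. But it answers a different question from the immediate effect, which the pre-session ratings, already collected, address directly.

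**Proportion.** This is a feasibility trial of 20 people with descriptive effect sizes and no hypothesis test. Neither Aim 2a nor 2b names carryover, and EMA does serve Aim 1 through completeness and burden. That limits the weight of the point and rules out asking for power or a formal carryover test. It does not supply an analysis for a purpose stated twice.

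**Weak checks.** The before-after EMA comparison is confounded with time trend, repeated rating and regression to the mean. Day 3 need not be the last EMA day, nor show the state at Visit 3, since follow-up is for at least 72 hours and no interval between the visits is fixed. This stands, and the fix is worded to respect it.

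**Conclusion.** The point holds in this form: a stated purpose of the follow-up EMA has no analysis, the washout goes unchecked, and the reference for immediate symptom and affect effects is not tied to the ratings taken just before each session. This should be corrected in the analysis text.

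The one structural result is that half of the mean residual at Visit 3 enters the two-session average if a pre-Visit 2 baseline is used. It assumes every subject completes both sessions. Its size in practice is unknown, because no carryover figure is given. The half-widths and SE ratios are illustrations under assumed variances and do not show that any planned result is biased.

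A reader might go further and infer that the washout is too short or that the dose comparison is biased by carryover. The documents show neither. They give no residual effect, and one that is equal for both doses cancels from the dose contrast when sequences are balanced.

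**What to change.** 1. Add to Aim 2 a descriptive within-subject comparison of mean post-session EMA with mean baseline EMA for pain, fatigue and affect, by dose, with 95% CIs. Add the last EMA day before Visit 3 against baseline as a washout check. State that both are confounded with time trend, repeated rating and regression to the mean, and are imprecise with 20 subjects.
2. Estimate the immediate symptom and affect effect from each visit's own pre-session rating, in line with the pre-session levels named for QST. Report change from the multiday EMA baseline alongside, labelled as change from typical level.
3. As a minor wording point, confirm in the Protocol section that the 72-hour EMA also follows Visit 3, as the Overview states.

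The cost is a few sentences and a small descriptive analysis of data already scheduled. The post-Visit 3 EMA is already promised: 9 prompts at under 5 minutes each, so under 45 minutes per subject over three days.

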#### *Analysis*

**Aim 1 - Feasibility:** We will identify the number of people from each referral source who contacted study personnel, volunteered to participate, and signed the consent. We will assess adherence to study protocols, including percentages completing outcome measures (including EMA) and completing both visits. We will assess IVR tolerance using the Simulator Sickness Questionnaire, pain threshold testing tolerance through direct questions, and the degree to which subjects felt engaged in the experience using the Igroup Presence Questionnaire. We

will determine how long it takes to complete the various parts of the study and how many breaks or incompletes occur during the intervention protocol. We will also examine expectations and perceptions of the IVR experience using open-ended questions.

*Aim 2 - Effect:* We will calculate effect sizes to compare baseline data to scores obtained immediately after completing IVR sessions. Symptoms and affect: We will examine the immediate effect of the IVR sessions by comparing the baseline symptom data with scores taken after completing the session. Tolerance to cutaneous sensory input: We will assess baseline and pre-session pain threshold levels with immediate post session measurements. To examine differences related to dosage, we will calculate an effect size between those who received the 10-minute IVR and those who received the 20-minute IVR session.

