## Grant Flow Chart

**Study Design:** This is a cross-over feasibility trial.

**Subjects:** We will recruit 20 people with chronic back pain.

**Inclusion/Exclusion criteria:** Inclusion criteria: 30 to 65 years old; Low Back Pain that has lasted greater than 3 months due to non-cancer related injury or illness. Exclusion criteria: People with back pain due to rheumatic (e.g. rheumatoid arthritis or fibromyalgia) or central neurological disorders (e.g. stroke, multiple sclerosis, spinal cord injury); vision to see IVR programs; insufficient upper extremity coordination to operate IVR controls; insufficient cognitive ability to answer questionnaires or learn to use the IVR; unable to understand and respond to English. Subjects must have access to a cell phone or tablet for baseline and follow-up EMA testing. There are no exclusion criteria based on sex, race, ethnicity, or sexual orientation.

**Recruitment:** Throughout the grant we will work with Tufts CTSI Recruitment and Retention Support Unit (RSSU) to devise customized, multi-modality strategies to minimize accrual time and maximize participant retention in research studies. Strategies include: 1) We will access the Brigham & Women's Chronic Pain Registry and mail letters to appropriate candidates. 2) We will query the Tufts Medical Center's Clinical Academic Research Enterprise Trust (CLARET) data warehouse to identify eligible patient population. The CLARET is a centralized clinical data warehouse that aggregates clinical information from various Tufts Medical Center's systems. 3) The Tufts Medical Center website publicly posts general information about all research studies so that people can identify and contact studies. 4) We will deploy targeted advertising using Facebook Ads; 5) We will place fliers/advertisement placed in the following CBP program waiting areas: Brigham & Women's, Tufts Chronic pain, Medford Chronic pain.

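### Do the words *completing* and *received* in Aim 2 drop subjects who stop IVR early and so flatter the 20-minute session?

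*Combined protocol and SAP*

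**What the plan says.** The trial is a small cross-over feasibility study: "We will recruit 20 people with chronic back pain", and "They will return for two counterbalanced IVR sessions: one 10-minute and one 20-minute". Randomization sets the order (Protocol): "Subjects will be randomly assigned to receive the 10 min or 20 min IVR session first".

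For Aim 2 the Analysis section says: "We will calculate effect sizes to compare baseline data to scores obtained immediately after completing IVR sessions". For symptoms and affect it repeats the idea as "comparing the baseline symptom data with scores taken after completing the session". The sensory-testing sentence refers only to measurements made straight after the session and does not mention completion. The dose comparison sets subjects who received the 10-minute session against "those who received the 20-minute IVR session".

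The plan expects that some sessions will be cut short. Aim 1 will count "how many breaks or incompletes occur during the intervention protocol", and the tolerance row under Outcome measures lists "minutes in IVR experience". No section says whether a session stopped early still contributes to Aim 2, or under which duration it would count. There is no stated analysis population or missing-data rule.

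**The concern.** The outcome is tied to completing the session and the dose contrast to what was received, while the same section treats incompletes as a category of their own. Taken word for word, a subject assigned 20 minutes who stops at 8 because of sickness or pain has neither completed the session nor received 20 minutes. That subject might be left out or reclassified.

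If stopping goes with a poor response and is commoner in the longer session, leaving such subjects out would inflate the pre/post effect and tilt the dose comparison toward 20 minutes. The effect analysis would then be selecting on tolerability, which Aim 1 is meant to measure, and the dose contrast would lose the protection of the randomized order. With 20 subjects, each one lost is 1/20 = 5% of the sample.

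**Working it through.** **Step 1: what the other sections say about measurement and dose.**

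- *Overview of Study*: symptoms and affect are measured straight after each session. The statement covers every session and sets no completion condition.
- *Protocol, Visit 2*: the IVR session is followed by ratings of pain, fatigue and affect and by sensory testing. None of these depends on reaching full duration. Visit 3 is to be the same.
- *Analysis, sensory testing*: measured after the session, with no completion condition. The literal reading therefore has no footing for one of the three outcome domains of Aim 2.
- *Protocol, randomization and Visit 2*: *receive* is the verb for the session assigned by randomization. The Visit 3 text uses *complete* in the same way, with the number of minutes set by randomization.
- *Design*: every subject is scheduled for both durations, so the dose phrase reads most naturally as a label for the scheduled session. Nothing suggests regrouping by minutes used.

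Taken together, *completing* is a time point and *received* is the duration assigned for that visit. No sentence excludes or reclassifies anyone.

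**Step 2: how large the bias would be under the literal reading.** The documents give no stopping rate, standard deviation or expected effect, so there is no planned figure to reproduce. The inputs below are assumptions, apart from n = 20.

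Let k of 20 subjects stop the 20-minute session and p = k/20. Mean improvement is dc = 0.50 in completers and ds in stoppers, in units of the within-group SD (set to 1). Then:

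- all-subjects mean m = (1 − p)·dc + p·ds
- all-subjects SD = √(1 + p(1 − p)(dc − ds)²)
- all-subjects d = m / SD, compared with 0.50 for completers only

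Worked case, k = 2, ds = 0: m = 0.9 × 0.50 = 0.45; SD = √(1 + 0.1 × 0.9 × 0.25) = 1.011; d = 0.45.

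| Stoppers' effect (ds) | d, k = 2 | d, k = 4 |
|---|---|---|
| −0.5 (worse) | 0.38 | 0.28 |
| 0 (no benefit) | 0.45 | 0.39 |
| 0.5 (same as completers) | 0.50 | 0.50 |
| 0.8 (larger benefit) | 0.53 | 0.56 |

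If nobody stops (k = 0) the two analyses are identical.

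**Step 3: the adverse illustration on a points scale.** Suppose completers change by −1.0 point (improvement) and stoppers by +1.0. The mean for all assigned is [(20 − k)(−1.0) + k(+1.0)]/20, which is −0.9, −0.8, −0.7 and −0.6 for k = 1 to 4. The completers-only figure stays at −1.0, so the gap is 0.1 to 0.4 points. The arithmetic is right, but it assumes that every stopper worsens by as much as completers improve. Reading it as a tilt toward 20 minutes further assumes that nobody is excluded from the 10-minute session; similar exclusions there would offset it.

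**The case for a change.** The best argument for a change is that the strict reading is not far-fetched. The Protocol attaches *complete* to a number of minutes, and Aim 1 uses *incompletes* as a category, so an incomplete session has, in plain language, not been completed. With no analysis population defined, an analyst could exclude early stoppers and claim to have followed the text. A longer session gives more time in which to stop. In the adverse rows of the table the shift would matter to a study meant to estimate magnitude of effect, and one sentence written before data are seen would cost almost nothing.

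The gap itself stands: the plan has no explicit early-stop rule. The rest is weaker. The Protocol sentence linking completion to minutes refers to the duration set by randomization, which supports analysis by assignment. The direction of bias is a conjecture, because no section gives stopping rates by duration or outcomes in stoppers. Nor would rewording recover data from a subject too unwell to be measured, since post-session testing would still need that subject's agreement. For a subject who can be measured, the Overview of Study and the Protocol already call for the measurement.

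**Conclusion.** No change follows. This is a gap in detail that analysts would fill sensibly: measure after each session, analyse by the duration assigned for that visit, and report minutes used alongside. The Overview of Study and the Protocol already point that way.

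On the assumed inputs (completers-only d = 0.50, 2 or 4 of 20 stopping), a completers-only analysis would overstate the 20-minute effect by up to 0.12 (k = 2) or 0.22 (k = 4) if stoppers worsen by 0.5 SD. It would make no difference if they respond like completers, and would understate the effect by 0.03 or 0.06 if they gain 0.8 SD. The documents do not determine which case applies.

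The consequences are also limited. Aim 2 produces descriptive effect sizes in 20 subjects, with no hypothesis test or efficacy decision rule stated. Breaks, incomplete sessions, minutes in IVR and simulator sickness are all collected as feasibility measures, so poor tolerance of the longer session would be visible to readers. This conclusion rests on reading *completing* as a time point and *received* as the assigned duration. It would need revisiting only if the analysts intended to exclude or regroup early stoppers, and nothing in the documents says that they do.
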